### **7.2 Study Procedures**

### **7.2.1 Baseline survey- Week 0**

Once a participant has been identified, recruited, and consented as described above, she will complete the baseline survey with a member of the study team via phone. After completion of the baseline survey, the participant will receive a thank you letter from the study team.

### **7.2.2 Randomization- Week 0**

Once a participant has completed the baseline survey, she will be randomly assigned to either the control arm or the intervention arm by a member of the study team. A simple randomization scheme, with 1:1 randomization, will be used to ensure equal sample sizes in the intervention and control arms.

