#### **4.2.4 Describe the eligibility screening process and indicate whether the screening process will occur before or after obtaining informed consent. Screening begins when the investigator obtains information about or from a prospective participant in order to determine their eligibility. In some studies, these procedures may not take place unless HIPAA Authorization is obtained OR a waiver of HIPAA Authorization when applicable for the screening procedures**

is approved by the IRB. [For FDA regulated studies, consent for any screening activities would need to be obtained prior to screening unless specifically waived by the IRB.]

A member of the study team will contact potentially-eligible women by phone to discuss the study, screen for eligibility, and obtain verbal consent from interested individuals.

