## 5.2 Obtaining Informed Consent

### 5.2.1 Timing and Location of Consent

Participants will be consented by a member of the research team over the phone, after eligibility is confirmed, using the Summary Explanation of Research. Participants will have previously received a copy of the Summary Explanation of Research in the mail with recruitment materials.

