### **7.4.5 Blinding of the Test Articles**

Not applicable.

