## **8.0 Subject Numbers and Statistical Plan**

### **8.1 Number of Subjects**

We plan to contact 500 potentially-eligible women via mail and email using the initial invitation letter. Of these, 220 are planned to consent and complete the baseline survey. From this 220, 110 will be randomized to the control group and 110 will be randomized to the intervention group. We expect about 10% loss to follow-up over the study period.

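### The team that screens, consents and surveys women also assigns the arm, no allocation concealment is described, and the simple scheme named cannot deliver the equal arms promised

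*Combined protocol and SAP*

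**What the plan says.** Four steps before and at assignment all belong to the study team.

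- **Screening and consent (4.2.4):** "A member of the study team will contact potentially-eligible women by phone to discuss the study, screen for eligibility, and obtain verbal consent". Section 5.2.1 adds the order: "Participants will be consented by a member of the research team over the phone, after eligibility is confirmed".
- **Baseline (7.2.1):** "she will complete the baseline survey with a member of the study team via phone".
- **Assignment (7.2.2, repeated in 7.4.3):** "she will be randomly assigned to either the control arm or the intervention arm by a member of the study team", after the baseline survey is complete.
- **Scheme (7.2.2 and 7.4.3):** "A simple randomization scheme, with 1:1 randomization, will be used to ensure equal sample sizes in the intervention and control arms".

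Section 8.1 then plans that "110 will be randomized to the control group and 110 will be randomized to the intervention group". Section 7.4.5, headed "Blinding of the Test Articles", is answered as not applicable. The arms are in any case visibly different (a letter against a parcel of kits), so the trial is open.

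Section 7.4.3 is where the method of assignment is meant to be described. Neither it nor 7.2.2 names a sequence generator, a list holder, a central system, sealed envelopes or a separation of roles. Both sections read as complete, so the gap does not look like removed text. Section 3.3.2 allows withdrawn women to be replaced and does not say how the replacement's arm is set.

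**The concern.** Concealment is a separate matter from blinding, and it is feasible in an open trial. It keeps the person who decides on entry from knowing the next arm. Without it, a caller who knows what is coming can apply the judgement-based criteria more or less strictly (communicating well in English in 3.1, cognitive impairment in 3.2). The caller can also work more or less hard to obtain consent and a completed baseline survey of about 45 minutes (7.3). Finishing that survey triggers assignment, so its timing also decides which woman takes which slot.

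The outcome is whether women get screened, and that plausibly depends on motivation. If enrolment depended on the coming arm, the arms could differ in motivation from the start. Both co-primary comparisons would then be biased, and the Fisher's exact test in 8.3 cannot correct for it. Section 8.2 intends the observed rates to inform later powered studies, so a biased difference would carry forward.

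**Working it through.** **1. The plan's own figure.** Inputs from 8.1 and 8.2: 110 per arm, 40% against 20%, two-sided Fisher's exact test, 2.5% type-1 error per endpoint. Summing the probabilities of all rejecting tables over two independent binomials gives power of 81.3%, against the stated 80%. The figure reproduces. Concealing the sequence does not change it.

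**2. Does a simple 1:1 scheme ensure equal arms?** The intervention arm size is Binomial(220, 0.5).

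- P(exactly 110) = C(220,110) / 2^220 = 0.0537, or 5.4%.
- SD = √(220 × 0.25) = 7.42. The normal range 110 ± 1.96 × 7.42 is 95.5 to 124.5; the exact 2.5% and 97.5% quantiles are 95 and 125.

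Equal arms are therefore not ensured. Reaching 110/110 reliably needs some restriction that the protocol does not describe.

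**3. What if the restriction is to close an arm at 110?** This is an assumption; no section states it. One arm reaches 110 when the other holds j women, with probability 2 × C(109 + j, j) / 2^(110 + j). The remaining R = 110 − j assignments are then all known.

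- Mean of R = 220 × C(220,110) / 2^220 = 220 × 0.0537 = 11.8, or 11.8/220 = 5.4% of assignments.
- Median 10, 90th percentile 24, P(R ≥ 20) = 18%.

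**4. How far could that move a screening rate?** All the forced assignments fall in one arm, and either arm is equally likely. On average they make up 11.8/110 = 10.7% of it; at the 90th percentile, 24/110 = 21.8%. The shift in that arm's rate is (share selected) × (difference in screening rate between selected and other women). The documents give neither factor. If every forced slot were filled selectively, a 5-point shift would need a difference of 5/0.107 ≈ 47 points on average, or 5/0.218 ≈ 23 points at the 90th percentile.

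For scale only, take an assumed selection difference between arms, no true effect and a 20% mean rate. Per-endpoint rejection at 110 per arm is 1.7% with no difference, 7.2% with 5 points and 29.7% with 10 points.

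**5. Cost of leaving the arms unequal.** The enumeration of step 1 at 95 and 125 women gives power of 82.8% (95 in the intervention arm) or 82.0% (125 in it). That is no worse than 81.3% at 110/110; the small rise comes from the discreteness of the exact test. Power gives no reason to force equality.

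**The case against.** The case on the other side is substantial. The protocol never says that a list is visible, or even that one exists before enrolment. Read literally, "Once a participant has completed the baseline survey, she will be randomly assigned" puts the draw after eligibility, consent and baseline. Under true simple randomization, past assignments say nothing about the next. Section 8.1's 110 and 110 can be read as planning counts, since no arm-closing rule accompanies them. Each step names a member of the team, so the overlap is shown for the team and not for one person.

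The room for steering is also limited. A health-center employee identifies women, sends invitations and makes any non-response calls (4.1, 4.2.1), and interested women then contact the team (4.2.3). Most criteria in 3.1 and 3.2 are factual.

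All of this stands, and it limits the claim. A reader might infer that callers can see the next assignment, that the caller is the assigner, or that a bias of some given size is to be expected. The documents support none of these. What the objection does not remove is that order is not concealment: assignment after baseline prevents reaction to an arm already given, not foreknowledge of the next. Nor can the protection of a simple scheme be relied on when the same sentence promises an equality that such a scheme does not give.

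**Conclusion.** The point holds as a weakness in the stated method. The enrolling team assigns the arm, no concealment is described, and the scheme named gives the planned 110/110 split only 5.4% of the time. Whether any assignment is predictable depends on practice that the protocol leaves open. Under the assumption that an arm is closed at 110, about 12 of 220 assignments are known in advance on average (90th percentile 24). By that route alone, a shift of several points would need strong selection. A larger effect would need a visible or controllable sequence, which the documents do not state. The size of any bias cannot be estimated from them. The change is still worth making before enrolment, because it is cheap, it protects both co-primary comparisons, and concealment cannot be restored afterwards.

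**What to change.** In 7.2.2 and 7.4.3, replace assignment by a team member with wording to this effect: a computer-generated sequence is held in the study database's randomization module, or an equivalent concealed system; staff who screen, consent or survey cannot view it; the system releases one time-stamped, irreversible assignment only after eligibility, consent and the completed baseline survey are recorded.

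State that no arm is closed by hand at 110, and choose one of two schemes:

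- randomly varying block sizes, hidden from callers, to obtain near-equal arms; or
- simple randomization, with the claim that it ensures equal sizes deleted and 110 per arm in 8.1 given as the expected number.

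State also that women who replace withdrawals (3.3.2) are assigned through the same system.

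The cost is protocol wording and a one-time set-up, with no new staff, contacts or participants and no change in the planned sample size. The small downside is the loss of manual override. If concealment is already practised, a few sentences saying who generates the sequence, who can see it and when it is released would close that part; the equal-size claim would still need correcting.

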### **7.2.3 Control arm- Week 1**

Participants randomized into the control arm will be mailed a standardized letter informing them that they are out-of-date for both cervical and colorectal cancer screenings and should schedule an appointment with their provider to receive these screenings.

### **7.2.4 Intervention arm- Week 1**

Participants randomized into the intervention arm will be mailed cervical and colorectal cancer self-sampling kits, instructions for completing the self-sampling kits, a lab requisition form, and educational materials about cervical and colorectal cancer. Participants will also receive an intervention cover letter that describes the contents of the package and what they are being asked to do. Participants will be asked to complete both cervical and colorectal cancer self-sampling kits within 3 days of each other via the intervention cover letter. Once complete, participants will mail the kits within 3 days of completing both tests to the Penn State Hershey Clinical Labs in a prepaid mailer provided by the study team. Notably, deviations from the timing of sampling and returning the test kits is quite flexible, since studies show that these samples are stable for up to 28 days.

#### **7.2.4.1 Reminder postcard- Week 6**

Participants who have not completed and returned both their cervical and colorectal cancer self-sampling kits within 6 weeks of receipt of kits will be mailed a reminder letter from the study team.

### **7.2.5 Follow-up survey- Week 10**

Participants will complete the follow-up survey with a member of the study team via phone. This will occur regardless of whether the participant was in the intervention or the control arm, and regardless of whether the participant completed and returned the self-sampling kits if in the intervention arm.

## **7.3 Duration of Participation**

Participants will be considered enrolled in the study from the time of consent until the completion of the follow-up survey. We anticipate a total participation of approximately 1 hour and 35 minutes for those in the intervention arm over the course of 10 weeks; this includes ~45 minutes to complete the baseline survey, ~20 minutes for the follow-up survey and up to ~15 minutes to complete each cervical

and colorectal cancer screening test kits. We anticipate a total participation of approximately 1 hour and 5 minutes for those in the control arm, over the course of 10 weeks; this includes ~45 minutes to complete the baseline survey and ~20 minutes for the follow-up survey.

## **7.4 Test Article(s) (Study Drug(s) and/or Study Device(s))**

### **7.4.1 Description**

The Evalyn® Brush is a self-sampling kit that screens for HPV, a leading cause of cancer death among women. This tool has recently been FDA approved, but has not been incorporated into national clinical guidelines. This product is a small pink capped brush that can be used to take a sample of cervical cells.

The InSure® test (Fecal Globin by Immunochemistry) is a fecal occult blood test that detects human hemoglobin from blood in fecal samples. The test is recommended for use by healthcare professionals to screen for colorectal cancer.

### **7.4.2 Treatment Regimen**

Participants will take a sample of their cervix cells that amounts to a few millimeters of bio specimen.

Participants will collect a fecal sample from toilet water using the provided tools and brush the sample on the InSure® FOBT test card.

### **7.4.3 Method for Assigning Subject to Treatment Groups**

Once a participant has completed the baseline survey, she will be randomly assigned to either the control arm or the intervention arm by a member of the study team. A simple randomization scheme, with 1:1 randomization, will be used to ensure equal sample sizes in the intervention and control arms.

### **7.4.4 Subject Compliance Monitoring**

Subject compliance will be confirmed once their lab results are received from the Penn State Heath Clinical lab.

### **7.4.5 Blinding of the Test Articles**

Not applicable.

### **7.4.6 Receiving, Storage, Dispensing and Return**

#### **7.4.6.1 Receipt of Test Article**

HPV self-sampling kits (Evalyn Brush, Rovers Medical Devices) are purchased from the manufacturer and shipped to the PI's office at Penn State Health. The study test article will be mailed to each participant in the intervention arm in original, unopened packaging, including 1 brush, 1 protective cap, 1 container/package for the brush, and 1 plastic bag for return mailing. The mailing will also include a lab requisition form (including a unique participant ID) to link each participant with their returned test kit.

FIT kits (InSure test, Fecal Globin by Immunochemistry) are purchased through Quest Diagnostics and shipped to the PI's office at Penn State Health. The study test article will be mailed to each participant in the intervention arm in original, unopened packaging, including 1 sample card, 1

collection brush, 1 self-adhesive label, and 1 reply form. The mailing will also include a lab requisition form (including a unique participant ID) to link each participant with their returned test kit.

The mailing will also include a pre-stamped and pre-addressed return shipping container for the participant to use to mail both kits to the PSH Clinical Lab. The unique participant ID will also be printed on this envelope and other participant materials.

#### **7.4.6.2 Storage**

Before HPV self-sampling kits are sent to study participants, they will be stored in a locked cabinet in the Department of Family and Community Medicine offices at [name]. Kits mailed to the lab will be disposed of after analysis.

Before colorectal self-sampling kits are sent to study participants, they will be stored in a locked cabinet in the Department of Family and Community Medicine offices at [name]. Kits mailed to the lab will be disposed of after analysis.

#### **7.4.6.3 Preparation and Dispensing**

Before it is sent to the participant, the Penn State Heath Clinical lab Pathology Services Special Account Requisition documents will be labeled with the participant's study ID #, date of birth, and sex (as required by the Requisition form). The mailing will include the HPV self-sampling kit with the instructions, the colorectal cancer self-sampling kit with the instructions, a Penn State Heath Clinical lab Pathology Services Special Account Requisition form, educational materials regarding the use of home cancer screening kits, and an intervention cover letter.

The package will also include a prepaid and labeled mailing to send the kits and Pathology Services Special Account Requisition documents to the Penn State Heath Clinical lab. Participants will need to include the date and time of sample collection on the requisition form.

#### **7.4.6.4 Return or Destruction of the Test Article**

HPV self-sampling kits will not be returned to participants. The samples will be analyzed and the kits will be destroyed by the Penn State Heath Clinical lab once analysis is complete.

Colorectal cancer self-sampling kits will not be returned to participants. The samples will be analyzed and the kits will be destroyed by the Quest Diagnostics once analysis is complete.

#### **7.4.6.5 Prior and Concomitant Therapy**

Not applicable.

## **8.0 Subject Numbers and Statistical Plan**

### **8.1 Number of Subjects**

We plan to contact 500 potentially-eligible women via mail and email using the initial invitation letter. Of these, 220 are planned to consent and complete the baseline survey. From this 220, 110 will be randomized to the control group and 110 will be randomized to the intervention group. We expect about 10% loss to follow-up over the study period.

### **8.2 Sample size determination**

This is a pilot study to approximate the rates of colorectal and cervical screening in the two study arms. Should the intervention yield a screening rate of 40% and the control arm a screening rate of 20%, then the proposed sample sizes yield 80% power based on a two-sided Fisher's exact test and a 2.5% type-1 error rate (allowing for two co-primary endpoints). The results of this pilot study will inform us with more accurate assessments of these screening rates so that future, more accurately powered studies can be conducted.

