#### **3.3.2 Follow-up for withdrawn subjects**

The withdrawal will be documented and the subject will be replaced if the timeline allows.

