### **8.3 Statistical methods**

The statistical analysis of study outcomes will primarily be descriptive. Outcomes will be assessed via the baseline and follow-up surveys, and whether or not self-sampling kits were returned by participants in the intervention arm. The main outcome is the differences in overall cervical cancer screening rate and the overall colorectal cancer screening rate at the end of the study between the two arms. Analysis of the main outcomes will be evaluated with a Fisher's exact test. Demographics of the patients in the two groups will be compared.

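### The 80% power in section 8.2 fits the full 110 women per arm; after the 10% loss expected in section 8.1 it is about 76–78%

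*Combined protocol and SAP*

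**What the plan says.** - **Section 8.1 (Number of Subjects)** sets the sizes: "From this 220, 110 will be randomized to the control group and 110 will be randomized to the intervention group". It then adds: "We expect about 10% loss to follow-up over the study period".
- **Section 8.2 (Sample size determination)** assumes screening rates of 40% (intervention) and 20% (control) and states that "the proposed sample sizes yield 80% power", "based on a two-sided Fisher's exact test", with a per-endpoint type I error of 2.5% because there are two co-primary endpoints. It mentions no loss, no evaluable number and no inflation.
- **Section 8.3 (Statistical methods)** names the same test for the analysis: "Analysis of the main outcomes will be evaluated with a Fisher's exact test". Outcomes come from the baseline and follow-up surveys and from "whether or not self-sampling kits were returned by participants in the intervention arm". The section does not say how women without a follow-up survey are handled.
- **Section 3.3.2 (Follow-up for withdrawn subjects)** says of a woman who withdraws that "the subject will be replaced if the timeline allows".

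**The concern.** The power statement and the loss assumption stand in adjacent subsections but do not meet. The only sizes that section 8.2 can refer to are the 110 and 110 randomized, yet the plan expects outcome data on about a tenth fewer women. A control woman who misses the week-10 survey has no other stated source for her outcome.

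If the 80% belongs to the randomized number, the chance of missing a true 40% versus 20% difference on an endpoint is larger than the 20% the reader is led to assume. That matters mainly when a non-significant result is interpreted.

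**Working it through.** **Inputs.** Rates 0.40 and 0.20, alpha 0.025 two-sided and Fisher's exact test (section 8.2); 110 randomized per arm and about 10% loss (section 8.1).

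**Expected evaluable number.** 220 × 0.10 = 22 lost; 220 − 22 = 198 evaluable; 110 × 0.90 = 99 per arm.

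**Method.** Exact unconditional power, by full enumeration:

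Power = Σₓ Σᵧ Bin(x; n₁, 0.40) · Bin(y; n₂, 0.20) · 1{p(x, y) ≤ 0.025},

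where p(x, y) is the two-sided Fisher p-value. Two definitions are in common use: summing all tables no more probable than the one observed (probability-ordered), and doubling the smaller tail (doubled). The plan does not choose between them. They agree when the arms are equal and differ when they are not.

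**Step 1: reproduce the plan's figure.** At 110/110 the power is 81.3%. The stated 80% is therefore a fair rounding for the full randomized number.

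**Step 2: equal arms of other sizes.**

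| Evaluable per arm | Power |
|---|---|
| 110 | 81.3% |
| 107 | 80.2% |
| 106 | 79.6% |
| 99 | 76.3% |

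So 80% needs at least 107 evaluable per arm.

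**Step 3: loss that is not exactly equal.**

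| Scenario | Probability-ordered | Doubled |
|---|---|---|
| Independent 10% loss in each arm of 110, average | 78.2% | 76.2% |
| 198 evaluable, random split, average | 78.0% | 76.2% |
| 198 evaluable, range over all splits from 88/110 to 110/88 | 76.3–79.2% | 74.7–77.4% |

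No split of 198 evaluable women reaches 80% under either definition.

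**Step 4: how many losses would have to be recovered.** Averaged over random splits, power reaches 80% at 207 evaluable women (80.3%; 79.8% at 206) with the probability-ordered p-value, and at 214 (80.1%; 79.8% at 213) with the doubled one. That means recovering 207 − 198 = 9 or 214 − 198 = 16 of the 22 expected losses.

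**Step 5: other ways to treat the lost women.**
- All intervention women recovered through kit return, control loses 10% (110/99): 80.7% probability-ordered, 78.7% doubled.
- All 110 per arm kept and lost women counted as not screened: the rates become 0.40 × 0.90 = 0.36 and 0.20 × 0.90 = 0.18, and power is 74.4%.

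**Step 6: could loss already be built in?** The uncorrected pooled two-proportion formula is

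Power = Φ{[0.20 − 2.2414 × √(2 × 0.30 × 0.70 / n)] / √[(0.24 + 0.16) / n]}.

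At n = 99 this is Φ{(0.20 − 0.1460) / 0.0636} = Φ(0.850) = 80.2%; at n = 98 it is 79.8%. That formula needs 99 per arm, and 99 / 0.90 = 110.

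**The case against.** The strongest reply is that the sentence in section 8.2 is literally true: the proposed sizes are 110 and 110, and the named test has 81.3% power there. On this view the plan only fails to say whether its 80% is before or after loss. That stands as a description of the wording. But a power figure is read as what the study will deliver, and the plan itself expects not to analyse 110 per arm.

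Second, loss to the survey need not mean loss to the analysis. Kit return is known for every intervention woman, and at 110/99 the probability-ordered test keeps 80.7%. This is a fair point, but it is the best case and still borderline: the doubled p-value gives 78.7%. Kit return also misses a clinic screening in a woman who returned no kit and did not answer the survey, and it does nothing for the control arm.

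Third, withdrawn women may be replaced. That depends on the timeline, and section 3.3.2 speaks of withdrawal, not of women who cannot be reached for the survey.

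Fourth, the match in step 6 suggests that the authors may have allowed for 10% loss with a chi-square-type formula. This cannot be settled from the documents. If so, the figure belongs to a different test from the one that sections 8.2 and 8.3 name, and it would still need correcting.

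Finally, the gap is small and the study is a pilot. That is accepted, and it sets the grade of the point.

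**Conclusion.** The concern holds, as a minor one. With the test, alpha, rates and loss that the plan itself gives, power per endpoint is about 76–78%, not 80%: 76.3% at exactly 99 per arm, and 78.2% or 76.2% on average under random loss. The chance of missing a true 40% versus 20% difference is then about 22–24% instead of 20%.

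This assumes that women lost to follow-up have no usable outcome and that the loss is close to 10% in both arms. Partial recovery through kit return or replacement would bring power nearer 80%; counting lost women as unscreened would take it lower. Because the analysis is mainly descriptive and the study is meant to inform later ones, the effect is on how a non-significant result is read, not on whether the design is sound.

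**What to change.** Restate the power in section 8.2, for example:

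> With 110 women randomized per arm and about 99 evaluable per arm after 10% loss to follow-up, power is about 76–78% per endpoint for 40% versus 20% (two-sided Fisher's exact test, 2.5% type I error). If all 110 per arm are evaluable, power is 81%.

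The cost is one sentence and a slightly less favourable stated figure. Sample size, test, endpoints and analysis do not change, and no extra enrolment is needed for a pilot of this kind.

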### 1.2 Primary Study Endpoints

Differences in overall cervical cancer screening rate and the overall colorectal cancer screening rate at the end of the study between the two arms.

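### Testing the two co-primary endpoints by Holm at an overall 5%, rather than at a fixed 2.5% each, adds power without more participants if both screening rates improve.

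*Combined protocol and SAP*

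**What the plan says.** Section 1.2 names two primary comparisons between the arms: "Differences in overall cervical cancer screening rate and the overall colorectal cancer screening rate". Section 8.2 assumes 40% in the intervention arm and 20% in the control arm, one pair of rates with no distinction between the cancers. It claims "80% power based on a two-sided Fisher's exact test" at "a 2.5% type-1 error rate (allowing for two co-primary endpoints". Two endpoints at 2.5% each add to 5%, so this is a fixed Bonferroni split.

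Section 8.3 calls the analysis mainly descriptive and then says "Analysis of the main outcomes will be evaluated with a" Fisher's exact test. It gives no significance level, no order of testing and no statement of whether one significant endpoint is enough. No other section mentions a multiplicity procedure.

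Two further statements bear on the number analysed. Section 8.1 randomises 110 women per arm and adds "We expect about 10% loss to follow-up over the study period". Section 3.3.2 says of a withdrawal that "the subject will be replaced if the timeline allows".

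**The concern.** The fixed split spends 2.5% on each endpoint whatever happens on the other. Holm tests the smaller p-value at 0.025 and, if that is significant, the larger at 0.05. It controls the family-wise error at 5% under any dependence between the endpoints, so it needs no added assumption.

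Take p = 0.01 on one endpoint and p = 0.04 on the other. The fixed split declares only the first. Holm declares both, at the same family-wise 5%. Both kits go out in one package (section 7.2.4), and 8.2 uses one pair of rates, so improvement on both endpoints is the case the plan has in view. That is also the case in which Holm gains. At stake is power for the second endpoint, and so for a claim on both cancers.

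**Working it through.** **Inputs from the documents.** Two-sided Fisher's exact test, 40% against 20%, 2.5% per endpoint (8.2); 110 per arm and about 10% loss (8.1). With equal loss, no replacement and lost women excluded, 110 × 0.90 = 99 per arm. Because 3.3.2 allows replacement, 99 and 110 are treated as a range.

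**Assumptions not in the documents.** The 40% and 20% rates apply to both endpoints. The correlation φ between a woman's two outcomes is 0 to 0.9.

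**Step 1: the plan's own figure.** Exact power sums the two binomial distributions over all tables with Fisher p at or below the level.

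| Per arm | level 0.025 | level 0.05 |
|---|---|---|
| 110 | 0.8131 | 0.8794 |
| 99 | 0.7627 | 0.8418 |

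The stated 80% reproduces at 110 per arm.

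**Step 2: Holm with independent endpoints, exact.** Let a be power at 0.025 and b power at 0.05.

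- Per endpoint: a + (b − a) × a. At 99: 0.7627 + 0.0791 × 0.7627 = 0.823. At 110: 0.8131 + 0.0663 × 0.8131 = 0.867.
- Both endpoints: a² + 2a(b − a). At 99: 0.5817 + 2 × 0.7627 × 0.0791 = 0.702, against a² = 0.582 for the split. At 110: 0.769 against 0.661.
- At least one: 1 − (1 − a)² for both methods. At 99: 0.944.

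**Step 3: correlated endpoints.** 1,000,000 simulated trials per setting, using the exact Fisher p-values, at 99 per arm:

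| φ | per endpoint, split | per endpoint, Holm | both, split | both, Holm | at least one, either method |
|---|---|---|---|---|---|
| 0 | 0.763 | 0.823 | 0.581 | 0.701 | 0.944 |
| 0.3 | 0.763 | 0.817 | 0.614 | 0.722 | 0.913 |
| 0.6 | 0.763 | 0.810 | 0.650 | 0.745 | 0.874 |
| 0.9 | 0.763 | 0.799 | 0.709 | 0.779 | 0.818 |

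Every extra Holm rejection is a second one, so with equal effects the gain per endpoint is half the gain for both: (0.779 − 0.709)/2 = 3.5 points at φ = 0.9, and about 6.0 at φ = 0. Above 0.9 it falls further: about 2.9 points at 0.95, 2.0 at 0.98 and zero at 1.

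At 110 per arm, over φ = 0 to 0.9, Holm gives 0.867 to 0.844 per endpoint (split 0.813). For both endpoints the split gives 0.661 to 0.766 and Holm 0.769 to 0.828.

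**Step 4: equivalent sample size.** Fixed-split power is 0.796 at 106 per arm, 0.802 at 107 and 0.823 at 112. Holm's 0.799 to 0.823 at 99 per arm is therefore worth about 106 − 99 = 7 to 112 − 99 = 13 more evaluable women per arm.

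**Step 5: unequal effects, 99 per arm.**

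- Second endpoint 30% against 20%: power for the first is 76-78% (split 76%), for the second 29-31% (split 22%).
- Second endpoint with no effect: power for the first stays at 76%.

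In these unequal settings, the intervention-arm correlation cannot reach 0.9. It is capped at 0.80 (rates 40% and 30%) or 0.61 (40% and 20%).

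**Step 6: error rates, 99 per arm.**

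- Both endpoints null at 20%: family-wise error 2.3-3.2%, the same for both methods.
- One true effect: the null endpoint is declared significant in 2.5-2.9% of trials under Holm, against 1.6% under the split. Both are below 5%.

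**The case against.** The plan contains no error here: the split is valid and its power figure reproduces. The 2.5% stands in a sample-size section, and sizing at 2.5% is compatible with Holm, whose first step is 0.025. The study is a pilot with a mainly descriptive analysis, so an extra significance declaration matters less than good interval estimates, and intervals that match Holm are harder to construct. Positive correlation is likely, because the cover letter asks for both kits within 3 days of each other and they return in one mailer, so the gains at φ = 0 are the least plausible. A woman lost to the survey may still have a kit-return outcome, so 99 per arm may be pessimistic. Finally, if success requires both endpoints, each can be tested at 5% without adjustment. Power for both at 99 per arm would then be 71-80% (0.8418² = 0.709 at φ = 0), slightly above Holm's 70-78%.

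Most of this limits the size of the point without removing it. The 2.5% in 8.2 is the only multiplicity provision in the documents, and a plan that names a test, a level and a power needs a decision rule even in a pilot. The gain shrinks with correlation but reaches zero only at φ = 1, and at the planned 110 per arm it is still about 3 to 5 points per endpoint. The success criterion is genuinely unstated. Dividing alpha makes sense only if either endpoint suffices, so that is the natural reading, but the sponsor should confirm it.

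**Conclusion.** The point holds as an optional improvement. With both rates at 40% against 20% and φ from 0 to 0.9, Holm adds about 3 to 6 points of power per endpoint and about 6 to 12 points for both, across 99 to 110 evaluable women per arm. The family-wise guarantee is unchanged and no rejection is lost.

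The gain is conditional on an effect on the other endpoint, and it does not raise the chance of at least one significant result. Holm therefore does not replace an allowance for the expected 10% loss.

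**What to change.** State in 8.3 that the two endpoints are tested by Holm at a family-wise two-sided 5%: the smaller p-value against 0.025 and, if significant, the larger against 0.05. State also that a significant result on either endpoint counts as success, once the sponsor has confirmed that this is meant. Report each risk difference with a confidence interval, since the pilot's aim is to estimate rates.

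Two further options are not needed for the main change. Hochberg's procedure gives 82-83% per endpoint at 99 per arm but relies on positive dependence. Boschloo's exact test in place of Fisher's, with Holm, gives 83-85% per endpoint at 99 per arm, with family-wise error of at most 4.1% when both endpoints are null at 20%.

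The cost is a protocol revision limited to wording, made before outcome data are seen. Simultaneous intervals matching Holm are less simple than under the split. The null endpoint's error rises as shown in step 6, and to 3.4-3.9% if Boschloo's test is also used.
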